Randomization. The study biostatistician will generate a randomized sequence of treatment group assignments using stratified permuted-block randomization (random block sizes of 2, 4, 6) stratified by A1C >9.0% and ≤9.0%. Sequences will be stored at and delivered through the REDCAP study database at the UW. Research staff will obtain the next randomization once a potential study participant has been determined to be eligible and has signed the study consent form.

Vital signs, anthropometrics measurements, and demographic information will be collected, and participants will be asked to complete study surveys as further detailed below. Participants will be asked to use pedometers and keep them on their person as much as possible during waking hours. Baseline data will be collected no more than 3 weeks prior to the initiation of the DSMES curriculum, and pedometer data will be collected over 10 days immediately following the baseline study visit. Both groups will undergo blinded CGM with insertion by study personnel over the same 10 days following the baseline visit. Participants will then have a follow up visit from a Patient Navigator 10-14 days after the initial visit (detailed below) If less than 72 hours of CGM data is obtained at follow up PN visit participants will be asked to repeat blinded CGM. Participants will be asked to continue their customary dietary and exercise habits until initiation of the intervention

Follow-up study visits given in a community setting will be within an acceptable window for data collection and held at weeks 12+/-2 weeks and 24+/-2 weeks (Visits 2: end of education intervention and visit 3:12 weeks after education intervention. The same procedures will be completed as described in detail below. Visits 2 and 3 also may be held in the participant's home or Sea Mar clinic according to the participant's preference and be completed through a remote RC visit with a PN in person visit to complete blood pressure, weight circumference and weight and A1c. The study team will continue to contact withdrawn participants to conduct an interview regarding barriers to study engagement.

Study Procedures

The following procedures will be performed at baseline (visit 1), (Visit 2) and (Visit 3):

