Anthropometric and vital sign measurements: **Height** will be measured by a Stadiometer. **Weight** will be measured using a SECA Digital scale, and BMI (kg/m^2) will be calculated. **Waist circumference** will be measured using a flexible measuring tape. Participants will remain in a seated position for a minimum of 15 minutes prior to measurement of **resting heart rate** and **blood pressure** with an Omron Professional Digital blood pressure and heart rate monitor.

Concomitant medications: Participants will be instructed to bring all current medications (prescription, over the counter, and herbal or vitamin supplements) to each study visit. The research study coordinator will review and record these medications. Comorbidities: We will use patient self-report to document stroke, CVD (congestive heart failure, myocardial infarction, or coronary heart disease), peripheral vascular disease, peripheral neuropathy, renal disease, and retinopathy. Point of Care A1C: The DCA Vantage Analyzer tests for a quantitative determination of A1C in human whole blood and provides immediate test results from a finger prick of blood. If age <50 and female urine dipstick for pregnancy completed.

Pedometer: participants will be given a pedometer or if preferred use the one available on their smartphone. They will be asked to keep the pedometer or phone on them as much as possible during waking hours during the study. Data will be collected for 10 days after the first visit then for the 10 days prior for visits 2 and 3.

Continuous Glucose Monitoring:

Blinded CGM: All participants will undergo blinded CGM for 10 days at baseline a (2-4 weeks prior to start of education) and visit 3 (24 weeks [+/-2 weeks]). The blinded CGM- education group will also complete blinded CGM for 10-day period at the end of the education intervention (visit 2: study weeks12 [+/-2 weeks]). Participants can mail blinded CGM devices back in self-addressed postage-paid envelopes provided at the initial PN visit and devices will be provided at the first PN visit.

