CGM (DEXCOM G6): A continuous glucose monitor (CGM) is a way to measure glucose levels in real-time throughout the day and night. A tiny electrode called a glucose sensor is inserted under the skin by a skin prick to measure glucose levels in tissue fluid. A small plastic piece of tubing remains inserted in the skin. Typically, one cannot feel this tubing once inserted. It is connected to a transmitter that sits on top of the skin and is about the size of a quarter. It is attached or secured by medical tape to the wearer's skin. It is approved for use on the abdomen and has been shown to be effective for use on alternative sites such as upper buttock and arm for 10 days. The CGM either records the blood sugars and stores which we will then be mailed or returned at education session one or it sends the information via wireless radio frequency to a monitoring/display device or to a cellular phone so one can see their own data on their glucose, and we can download it remotely. The device automatically generates an alert for glucose < 55, and an alert will also be generated for glucose > 180 in the unblinded portion of the study. The intervention group participants will be given a handout (Appendix K) for troubleshooting these alerts, particularly during the blinded portion of the study. DEXCOM G6 is FDA approved for use in patients with diabetes and will be used in accordance with instructions as approved for diabetes. The risk is minimal with use of this device. In this study, we recommend patients connect the CGM to their cell phones. Study staff will insert the first sensor for the groups and then PN at digital navigation visit will demonstrate how to insert additional sensors for the intervention group who will continue to use RT-CGM and control group in case they need to self-insert blinded CGM. If this is to be done as a televisit, the sensors, transmitter, and device (if needed) will be mailed to the participant. Then the study staff will walk the participant through the first insertion through a virtual zoom visit. Patients will also have a YouTube video available for reference for the patients. The patients will be instructed on how to remove the sensor themselves after 10 days and bring it back or mail back. The RT-CGM-education intervention group will wear the RT-CGM- cyclically and have telephone support and may refer to the YouTube video on insertion if needed. The intervention participants will have RT-CGM download after 3 cyclic sessions of use and at 5 sessions of use. The Blinded-CGM education group participants will wear the blinded CGM at baseline and 24=/- weeks at conclusion of intervention. If, during the blinded portion of the study, due to device malfunction (rather than subject non-compliance), the device records less than 3 days of data, the participant will restart another 10 days of blinded CGM data.

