
The receiver and/or the app will display the glucose reading along with a rate of change arrow and a trend graph. Additionally, the receiver and/or app issues alarms and alerts to notify the patient of glucose level changes and other important system conditions. The app provides the additional capability to share data with "followers" using the Dexcom Share service.

CGM Ancillary Devices Dexcom CLARITY® is an accessory for users of the Dexcom CGM system. It is a software program that allows the transfer of glucose data from the CGM system to Dexcom remote servers for data management to allow the use of the CGM data by the user and study clinicians. Target ranges of 70 to 180 mg/dl will be set, and the patients will be introduced to the use of alarm settings. Both participants and study sites will use CLARITY® to transfer glucose data between user and study site, whether CGM is used in blinded or real-time mode. A CLARITY® mobile app can be used for a retrospective review of glucose data on the smart device and can also be set up to allow receipt of push notifications of CGM data facilitating data review. For all patients (intervention and control group) an anonymized CLARITY® account will be created by using a sequential study number which is allocated at randomization. Additionally, if participants desire The Dexcom G6 CGM System comes with a built-in Dexcom Share feature so you can let up to 10 people follow your glucose levels,

giving you a circle of support. By downloading the Dexcom Follow app, Followers can view your glucose data directly from their smart device

Intervention/ RT-CGM- education Group:

- For participants the DEXCOM G6 CGM app will be installed on participant's smart phone.
- An anonymized CLARITY® mobile account will be set up and linked to the research site.
- A high alert threshold will be set at 180 mg/dl and low alert threshold for <70mg/dl. In addition, the urgent low alert (55 mg/dl [3.1 mmol/l]), the urgent low soon alert (when glucose levels are falling fast and will be below 55 mg/dl [3.1 mmol/l] in less than 20 min) as well as alerts for rise and fall rate (3 mg/dl [0.17 mmol/l]) in addition to alerts for signal loss and no readings for more than 20 min will be enabled and patients will be shown how to turn off if they desire.
- Participants with applicable smart phones may have CLARITY® push notifications on the CLARITY® mobile app about weekly time in range comparison enabled during the study.

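### The handout for troubleshooting the under-55 mg/dL alert is assigned to the intervention arm only, although controls also wear blinded sensors

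*Combined protocol and SAP*

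**What the plan says.** The device paragraph (Medical Devices, CGM (DEXCOM G6)) states: "The device automatically generates an alert for glucose < 55". The same sentence adds an alert above 180 mg/dL and ties only that one to the unblinded part of the study. The next sentence reads: "The intervention group participants will be given a handout (Appendix K) for troubleshooting these alerts, particularly during the blinded portion of the study".

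Blinded wear is not confined to the intervention group. Section H (Randomization) has both groups wear a blinded sensor for the 10 days after the baseline visit, and provides for further wear if the recording is short: "If less than 72 hours of CGM data is obtained at follow up PN visit participants will be asked to repeat blinded CGM". Under Continuous Glucose Monitoring, Blinded CGM, all participants wear a blinded sensor at baseline and at visit 3, and the control group "will also complete blinded CGM for 10-day period at the end of the education intervention". The device paragraph gives a shorter control schedule, in which controls "will wear the blinded CGM at baseline and 24=/- weeks at conclusion of intervention".

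Two other items could reach controls:

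- **Training.** Preparation for the study intervention describes a 30-minute CGM session from the Patient Navigator. It is not limited to one arm, and its stated emphasis is on using real-time readings to understand eating and activity.
- **Educational handout.** The RT-CGM Handout paragraph describes material on glucose goals, food and activity, and assigns Appendix A2 to participants without real-time sensors. Section U lists A1 as the blinded-CGM material and A2 as the real-time material.

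**The concern.** The handout is meant mainly for blinded wear, when a participant can be alerted but cannot see a glucose reading. Controls are in that position for at least as many periods as the intervention group, yet the text names only the intervention group as recipients. Followed as written, a control participant whose sensor alarms below 55 mg/dL has no described study instruction on what the alarm means or what to do.

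What is at stake is participant safety during wear, to a modest degree. No estimate, test or power figure in the plan depends on it.

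**Working it through.** The plan states no figure on this point. The check is a comparison of sections, plus a count of planned wear.

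**1. Does the low alert apply during blinded wear?** The device paragraph calls the under-55 alert automatic and restricts only the over-180 alert to unblinded wear. It then says the handout matters most in the blinded portion, which presupposes that an alert can occur then. The detailed alert settings appear only under the Intervention/RT-CGM-education Group heading, and the control paragraph lists none. That controls' blinded sensors also alarm is therefore a reading of the device paragraph, though the natural one, since it describes one device for both arms.

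**2. What is each arm described as receiving?**

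| Item | Intervention | Control | Alert content described? |
|---|---|---|---|
| Appendix K | Yes | Not named | Yes |
| Patient Navigator CGM session | Yes | Yes, on its wording | No (emphasis on food and activity) |
| Educational handout A1/A2 | Yes | Yes, but label conflicts | No (glucose goals, food, activity) |

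**3. Timing of the training.** Baseline blinded wear covers days 0 to 10 after the baseline visit. Section H places the Patient Navigator visit 10 to 14 days after that visit. The session therefore comes after the planned baseline wear.

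**4. Size of the exposure.** Inputs: 50 per arm (Section S), 10 days per period, and the two control schedules quoted above.

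- Study Procedures schedule: controls 3 × 10 × 50 = 1,500 sensor-days; intervention 2 × 10 × 50 = 1,000. Control share = 1,500 / 2,500 = 60%.
- Device-paragraph schedule for controls: 2 × 10 × 50 = 1,000. Control share = 1,000 / 2,000 = 50%.
- Baseline wear alone, before any training: 10 × 50 = 500 control sensor-days.
- At the maximum enrollment of 120 (Section D), taken as 60 per arm: 2 × 10 × 60 = 1,200 to 3 × 10 × 60 = 1,800.

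Repeat wears under the 72-hour rule would add to these counts. All of them count planned wear. The documents give no rate of low glucose, so no number of affected participants follows.

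**The case against.** **Unseen material may cover this.** Appendices A1, A2, K, L and M are listed but their contents were not supplied, and consent pages were removed. Alert advice for controls could sit there. This stands, and it limits the claim to the protocol body. It does not remove the arm restriction or the A1/A2 conflict, both of which are in the text supplied.

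**The risk is low.** Entry requires A1C of at least 8.0%. Current prandial insulin and known hypoglycemia unawareness are exclusions. Controls test their own glucose as their primary care provider advises and keep a log. Blinded wear does not itself cause lows. This also stands, and it is why the point is minor. It does not explain why one arm should have the handout and the other not.

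**The label mismatch is clerical.** Agreed. The intended recipients are clear, but staff handing out A2 to controls as written would give them what the appendix list calls the real-time material.

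**A stronger inference.** A reader might conclude that the protocol is deficient because no one is assigned to read blinded recordings for lows and tell the primary care provider. It is true that the data reach the site: the software is used "to transfer glucose data between user and study site, whether CGM is used in blinded or real-time mode" and exists "to allow the use of the CGM data by the user and study clinicians", which is access and not a duty. The documents do not support calling this an error, for four reasons:

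- The 72-hour rule is an ordinary data-sufficiency rule and was not written to do this job.
- The unseen appendices may deal with it.
- Blinded devices may be mailed back or returned at session one, so a review would come after the event.
- Notifications could change care within a whole-cohort before-and-after analysis of A1C, and could also touch the 24-week between-group comparison. The size and direction of such effects cannot be fixed from the documents.

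Equal handling of the arms would not be automatic either. RT-CGM participants "will have RT-CGM download after 3 cyclic sessions of use and at 5 sessions of use". The first of those downloads has no control counterpart, and the second has one only if controls wear a sensor at visit 2, on which the two schedules differ.

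**Conclusion.** The point holds in a narrow form. The protocol body describes a low-glucose alert that is not limited to unblinded wear, but names only intervention participants as recipients of the handout explaining it. Controls have two or three blinded periods, or 1,000 to 1,500 planned sensor-days for 50 people, and no supplied section gives them alert guidance.

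This is a cheap, minor improvement in participant safety. It assumes that the under-55 alert is active on controls' blinded sensors, as the device paragraph implies, and that unseen appendices do not already supply the guidance. A duty to review blinded recordings and notify the provider is a choice for the investigators, not a required correction.

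**What to change.** 1. Amend the device paragraph so that Appendix K goes to all participants at the baseline visit, before the first blinded sensor starts. For remote visits, send it with the mailed sensors.
2. Make the RT-CGM Handout paragraph and Section U agree on which of A1 and A2 is the blinded-CGM material, so that controls receive that one.

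The cost is one extra existing handout for 50 controls, or 60 at maximum enrollment, and two small text edits. No effect on the analysis is expected. If the investigators also want recordings reviewed for lows, they should set the limit and response in advance and weigh the possible effect on care during the outcome period.

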Aim 1: Determine the impact of the *Compañeros en Salud* (Partners in Health) curriculum in conjunction with RT-CGM on glycemic control in Latinx patients with T2D. We will enroll 100 Latinx patients with uncontrolled T2D through a federally funded healthcare network across the Seattle region. Participants will be randomized to receive the *Compañeros en Salud* diabetes self-management education and support (DSMES) intervention with or without RT-CGM (n=50 per group) over 12 weeks with an additional 12 weeks of follow-up.(control= blinded -CGM+ Education and intervention= RT-CGM + education). Study visits will be held at screening, baseline(0-4 weeks) and 12 weeks (+/- 2 weeks) and 24 weeks (+/-2) weeks. Participants in the blinded -CGM+ Education group will undergo blinded CGM for 1 week at baseline and for 10 days after each study visit. The primary outcome will be A1C. Secondary outcomes will include time in range as measured by CGM and other CGM indices, body mass index, waist circumference, and systolic and diastolic blood pressure.

Aim 2: Engage key stakeholders to optimize acceptability and minimize barriers to participation in the intervention. After 25% of participants have completed the intervention, we will convene a committee of stakeholders that includes study participants (both completers and non-completers), community providers, diabetes educators, and patient navigators. Key barriers and facilitators to the intervention will be identified by stakeholders, and the intervention will be amended based on stakeholder feedback. The impact of these revisions on participant engagement during the study intervention will be analyzed.

Aim 3. Determine the effects of the *Compañeros en Salud* curriculum with or without adjunct RT-CGM on diabetes-related behaviors and distress. At baseline and 12-+2 weeks and 24 +/- 2 weeks, participants will complete surveys capturing dietary behaviors, physical activity, and diabetes-related distress. Participants will be provided with pedometers, and activity data will be captured for 10 days following each study visit. **Sub-aim 3A:** As an exploratory sub-aim, we will examine behavioral changes in other members of participants' households through brief surveys. This sub-aim will provide preliminary data regarding a possible "ripple effect," the capacity for an intervention in 1 individual to affect health-related behaviors in other household members.

B. Background

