Baseline Visit/Visit 1. Base line visit is 2-4 weeks prior to Week 1, which is the start of education intervention. Week 1 is the first week of the education sessions. Baseline visit will occur in the participant's home or at a local Sea Mar clinic and/ or maybe a combination of remote and in-person. A research coordinator will review the full informed consent document, explaining study goals, procedures, and any potential risks in Spanish or English. Consent (appendix Z ?) will be obtained prior to any screening procedures being completed, and conducted in a quiet room or private televisit. Participant will be given ample time to ask questions, and a copy of the signed consent form will be given prior to start of screening visit procedures. Participants will fill out a contact form, including emergency contact (appendix Z1). Study staff will review medical history and medications and family history (appendix D), as well as all inclusion/exclusion criteria. Point of care A1C will be measured via point of care testing with a Siemens DCA Vantage A1C Analyzer, at LabCorp or quest for serum A1C if remote visit is completed. All women of child-bearing potential will undergo a urine pregnancy test either point of care or at LabCorp. Participants who meet criteria for enrollment and wish to proceed with study participation will be randomized to an intervention arm in unblinded fashion.

Remote Consent : If baseline visit is remote/virtual, the consent form will be sent to the participant via REDCap to be viewed and signed remotely. Subjects can also request that a paper copy of the consent be mailed to them before Visit 1. The informed consent discussion includes time for the potential participant to read over the consent form and to think about their questions. If the potential participant has questions outside of the Research Coordinator's scope, the potential participant will be offered a follow-up consultation with the Principal Investigator or Co-Investigator who can provide more information. As this is a minimal risk study, we will request a waiver of documentation of consent.

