RT-CGM: Participants in the RT-CGM arm will be asked to wear the device for a total of 50 days for 84 days during the 12 weeks of education sessions at intervals of 10 days on then 7 days off over 12 weeks. CGM data for 10 days will be downloaded after the completion of the 3rd RT-CGM wear session which should correlate approximately with the 6th education session. The final period of RT-CGM use will begin on the day of the final session of the DSMES curriculum. Participants will undergo initial training by PN and can have assistance for the first device self-insertion and may request additional virtual, telephone, or in-person assistance from PN. In our experience, study participants readily assimilate the self-insertion technique and require negligible follow-up support for this procedure. RT-CGM data will be collected remotely using a cloud-based platform

Preparation for the study intervention: Patient Navigators (PN) from Sea mar health education team will engage participants no more than 2-4 weeks prior to the start of the DSMES intervention to ensure participants have a working technology platform for the education sessions and provide hot spot if able through one home visit with option for second if need to assess barriers to technology or attendance. For all participants, PN will teach simple CGM insertion (blinded and RT). For those who are enrolled in RT-CGM arm, the PN will set up a mobile app for the RT-CGM device. PN also will conduct a 1, 30-minute training session on CGM for participants in this study, with particular focus on the use of RT-CGM as a tool to understand food and activity choices. If RC is remote PN may also engage at visits 1, 2 and 3 to gather objective measurements (weight, blood pressure and POC A1C or participant may go to LabCorp/quest for the A1C) As well they well gather the 10 days baseline pedometer data

Study Procedures: Study Participants' Household Member: No protected health information will be recorded for household member. Demographics of relationship to study participant, age and sex and history of diabetes or prediabetes will be recorded at baseline visit. Email address maybe recorded in order to contact patients if verbal permission is given.

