***Approximate Total duration of CGM use would be 12 weeks goal 5 sessions 10 day wears over 12 weeks**

****measures appendix B**

Figure 2: Study Timeline

Timeline in 6 Month Intervals		01	02	03	04	05	06
Pre-Project Award							
Obtain IRB Approval							
Train research staff							
Intervention							
Recruit first 25 Participants							
Recruit 75 Participants							
Convene First Advisory Board							
Conduct Aim 1-3 and sub-aim							
Data Analysis & Dissemination							
Clean and manage data							
Analyze data							
Prepare manuscripts							
Project Phase	Pre	01	02	03	04	05	06

J. visits complete in home and clinic Sea Mar study visit within window, then the research visit will be scheduled via telehealth. The University of Washington uses the ZOOM platform which is HIPAA compliant and ensures patient privacy during the visit.

Study Intervention Materials and Devices :

Televisits:

Preference will be to conduct screening and all study visits in person at patient's home or at Sea Mar clinic. However as COVID-19 pandemic continues more patients are using telehealth visits for routine care. If patient is not able to

Medical Devices:

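### The week-12 CGM wear is timed by class 12 in the RT-CGM arm but by visit 2 in the control arm, so this secondary comparison can measure the arms at different times

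*Combined protocol and SAP*

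**What the plan says.** **RT-CGM arm.** Section H, Continuous Glucose Monitoring (RT-CGM), asks for wear "for a total of 50 days for 84 days during the 12 weeks of education sessions". The cycle prescribed there is "at intervals of 10 days on then 7 days off over 12 weeks". A later sentence of the same paragraph adds: "The final period of RT-CGM use will begin on the day of the final session of the DSMES curriculum". No visit window applies to that last wear. The Figure 1 footnote words the overall target loosely: "Approximate Total duration of CGM use would be 12 weeks goal 5 sessions 10 day wears over 12 weeks". The device description under Study Intervention Materials and Devices has the data downloaded after the third and fifth wears.

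**Control arm.** The opening Aim 1 text says that controls "will undergo blinded CGM for 1 week at baseline and for 10 days after each study visit". Section H (Blinded CGM) gives controls a 10-day wear when education ends and equates that with visit 2 at 12 ± 2 weeks. The device description names a baseline wear and then a garbled phrase that joins week 24 to the conclusion of the intervention. It does not clearly list a week-12 wear.

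**Calendar.** Section H (Baseline Visit) says "Week 1 is the first week of the education sessions", and section G makes the 12 classes weekly. Section H (Follow-up study visits) labels the second visit "Visits 2: end of education intervention" and allows ± 2 weeks. Section M (Logs) asks participants for optional food and activity logs over the 10 days after session 12.

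**Analysis.** Section N plans between-group comparisons of CGM change from baseline to week 12 and to week 24. Section E (Data Analysis Plan, Aim 1) lists the CGM indices for descriptive comparison and also names time in range among the secondary outcomes to be modelled. Its A1C model, which the secondary models are to follow, codes time as baseline, visit 2 and visit 3.

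**The concern.** The two arms use different clocks for what section N treats as one time point. The RT-CGM days follow the class calendar, while the control days move with the visit date. If sites follow the text, the arms can be measured at different distances from the end of education, and that difference is tied to arm. Randomization does not balance it, because it comes from the measurement rule. A model that labels both sets of days as visit 2 does not adjust for it.

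At stake is the week-12 between-arm comparison of time in range and the other CGM indices, all secondary. If glucose is still changing around the end of the classes, part of the apparent effect of RT-CGM could reflect timing.

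**Working it through.** **Inputs**

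- Day 1 = class 1. This is an assumption, based on week 1 being the first week of sessions (section H).
- Weekly classes (section G), so class *k* falls on day 1 + 7(*k* − 1).
- Visit 2 at week 12 ± 2 (section H), taken as day 84 ± 14 = days 70–98, which is 29 permitted days.
- Each wear lasts 10 days. The control wear is taken to start on the visit-2 day.

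**The plan's own figure.** Five wears × 10 days = 50 days. With four 7-day breaks the span is 50 + 28 = 78 days, which fits within 84. The stated total is reproduced.

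**RT-CGM week-12 wear.** Class 12 is on day 1 + 7 × 11 = 78, so the last wear covers days 78–87.

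**Control week-12 wear.** For a start on day *d*, the shift from the RT-CGM wear is *d* − 78, and the days in common are max(0, 10 − |*d* − 78|).

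| Visit 2 on day | Control wear | Shift (days) | Days in common |
|---|---|---|---|
| 70 (week 10) | 70–79 | −8 | 2 |
| 78 (class 12) | 78–87 | 0 | 10 |
| 84 (nominal week 12) | 84–93 | +6 | 4 |
| 98 (week 14) | 98–107 | +20 | 0 |

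The wears have no day in common when visit 2 falls on days 88–98, which is 11 of the 29 permitted days.

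**Other day counts**

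- Week 12 counted as day 85, or the control wear started the day after the visit: shift −7 to +21, 3 days in common at nominal week 12, none on 12 of 29 days.
- Class 12 placed on day 84: shift −14 to +14, all 10 days in common at nominal week 12, none on 10 of 29 days.

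Each count leaves a possible shift of two to three weeks in at least one direction.

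**Does the 10-on/7-off cycle fit the class-12 start?** The fifth wear starts 4 × 17 = 68 days after the first.

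- First wear on day 1: the wears are days 1–10, 18–27, 35–44, 52–61 and 69–78. The fifth ends on the day the class-12 sentence says it begins.
- First wear on day 78 − 68 = 10: the wears are days 10–19, 27–36, 44–53, 61–70 and 78–87. The cycle is exact, the total is 50 days and the last wear starts at class 12. The third wear then comes after class 6 (day 36), but the plan calls that link approximate.

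The plan does not state the day of the first RT-CGM wear, so the two instructions can be reconciled.

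**The case against.** The strongest reply is that the text already points both arms to the same time. Visit 2 is labelled as the end of education, section H places the control wear there, the last RT-CGM wear starts at the final class, and the optional logs cover the 10 days after session 12. On that view ± 2 weeks is ordinary visit tolerance, and a visit anywhere in days 78–84 shares 4 to 10 days with the RT-CGM wear. Figure 1 and the Appendix B measurement table were not available to this review and may set out the schedule. This stands as evidence of intent. It does not supply a rule: no readable section says which 10 days count as week 12, and only the control wear carries the visit tolerance.

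Three stronger readings are tempting, and the documents do not support them.

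- **That the control week-12 wear was dropped.** The sentence in the device description is garbled, and Aim 1 and section H both provide the wear. This is an inconsistency, not an omission from the plan.
- **That the days in common measure bias.** Each participant's time in range comes from their own 10 days, and arms can be comparable without sharing days. What matters is whether glucose shifts over the gap, and the documents give no figure for that. The counts of permitted days are not expected frequencies either.
- **That the RT-CGM schedule contradicts itself.** The clash requires a first wear at class 1, which the plan does not state.

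It is also fair to say that at week 12 one arm sees its glucose and the other is blinded, a difference that aligning the days does not remove. The week-24 comparison, with blinded wear in all participants, does not have that problem.

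**Conclusion.** The point holds as a timing inconsistency in a secondary comparison. Followed literally, the control wear can start from 8 days before to 20 days after the RT-CGM wear. These limits assume that class 1 is day 1, classes run weekly without slippage, week 12 is day 84 and the control sensor starts on the visit day. Other conventions move the limits but leave a gap. It is also inferred, not stated, that the fifth RT-CGM wear supplies that arm's week-12 data.

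The direction and size of any bias in time in range cannot be estimated from the documents. The primary inference, on A1C change to 12 weeks in the pooled cohort, does not use CGM data and is unaffected. The amendment is worth making because it is cheap and settles a question that section N leaves open.

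**What to change.** - In section N, state that the week-12 CGM window in both arms is the 10 days starting on the scheduled date of session 12. Using the scheduled date keeps the rule independent of attendance.
- Start the control blinded wear on that date, and make Aim 1, section H (Blinded CGM) and the device description agree. The device description should list a week-12 control wear explicitly.
- Leave the A1C visit window at 12 ± 2 weeks.
- Do not prescribe a new RT-CGM schedule. At most, ask the sponsor to confirm a first-wear day compatible with the class-12 start.

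**Cost.** These are wording changes, with no added sensors or scheduled visits. Section H already supplies control devices and return envelopes at the first patient navigator visit, and it provides the training: "For all participants, PN will teach simple CGM insertion (blinded and RT"). The real cost is that some controls must insert a sensor themselves on a day without a study visit. The device description foresees this only as a contingency, so some control data could be lost.
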